## **Clinical Investigation Duration (Per subject):**

Screening + Standard-of-Care (SOC) Run-in + Treatment + Safety Follow-up.

- Screening & Run-in SOC: (14 days (± 2 days)).
- Treatment: 28 Days total
  - O Safety and Efficacy evaluations: 7 days (±2 days); 14 days (±2 days); 21 days (±2 days); 28 days/EOT (±2 days).
- Safety Follow-up: 42 days (± 2 days) after first treatment

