#### Administration

Gel (Commercially acquired Hydrogel from V1 to V3 and after V7 through V8. Test Product gel between V3 and V7) will be applied topically to the target ulcer twice daily, roughly every 12 hours at the same times of day for four weeks during the entire study. Optimum evening treatment would occur at bedtime, once the subject is in bed for the evening. After application of each dose of the Test Product is complete, the wound will be dressed as per the following: Mepitel or equivalent will be trimmed to cover the entire dimension of the ulcer and overlaid into the ulcer, followed by Tegaderm dressing covering the entire dimension of the ulcer. Padding and Coban Lite 2- layer dressing or equivalent will be placed over the Mepitel covered with Tegaderm. Application of Test Product or any gel should not occur on the day of V7, or on the day of an early term visit. During the treatment phase, no gel other than Test Product can be administered.

Standardization of various processes are essential including subject/caregiver instruction; debridement; offloading; wound measurement/ digital imaging, digital photography and microbiological sampling and analysis as described in various appendices.

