# 4. OJECTIVE AND ENDPOINTS

	Objective	Endpoint [at 28 days]	Variable			
Primary	•To assess the safety and tolerability of escalating doses of topically applied Bisphosphocin Nu-3 Gel	Treatment emergent events related to clinical investigational product	
 
Vital signs
 
Safety laboratory analysis
 
Local wound/skin assessments
 
Physical examination
 
Adverse events
 
			
Secondary	
 
To assess the clinical effects of Nu-3 on cDFU
 
To assess antimicrobial effects of Nu-3 on wound microflora.
 
To support determination of the appropriate dose range of Nu-3 to be employed in future clinical studies.
 
	
 
Advanced digital imaging wound assessment post debridement
 
Pre and Post debridement digital pictures taken by clinical staff.
 
Changes in wound microbial population pre debridement
 
Recommended Phase 2 Dose (RP2D)
 
	
 
Ulcer surface area
 
Ulcer depth
 
Culture and microflora microbiological analysis
 
			

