## 7.1. Treatments Administered

Study Treatment Name:	Bisphosphocin®	Placebo		
Dosage formulation:	Gel	Gel		
Unit dose strength(s)/Dosage level(s):	5% or 10% concentration	Not applicable		
Route of Administration	Topical administration	Topical administration		
Dosing instructions:	Gel to be applied twice daily (BID) for 28 days	Gel to be applied twice daily (BID) for 28 days		
Packaging and Labeling	Test Product kits will be labelled and contain 18 applicators individually packaged in a foil pouch. These kits will be prelabelled with Batch/Expiration Dating/study and kit ID numbers. used for dose administration.	Matching placebo kits will be labelled and contain 18 applicators individually packaged in a foil pouch. These kits will be pre-labelled with Batch/Expiration Dating/study and kit ID numbers. used for dose administration.		

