- Take digital images with sponsor provided camera both pre and post debridement, if debridement is required. Two photos are to be taken from a focal distance of 18 inches, and one photo taken

- close-up for a total of three digital images
- Employ an advanced digital imaging system to accurately measure the target foot ulcer dimensions following debridement (if debridement is performed, only light debridement may be performed).
- Two wound swabs, one for culture and one for microflora examination are taken BEFORE debridement, if the wound is still open
- Collect kit dispensed on Day 14, determine accountability
- Subjects will be provided with his/her fourth and final designated test product kit and instructed to apply the product twice daily for 1 week (7±2 days).
- The subject will be scheduled for the next study visit, with a reminder to bring the test article kit and all tubes including empty, partially used and unused tubes to the visit.
- Record all adverse events (local and systemic), concurrent procedures, and changes in concomitant medications during the study on the source documents and case report forms (eCRFs).
- Continue offloading applied in accordance with Appendix 6

Visit 7 (Day 28±2 days): The study subject will return for final efficacy evaluation to the clinical site on Day 28±2 days. At that visit, the subject will undergo the following procedures and evaluations.

- Vital signs measurements: Weight, temperature, resting blood pressure, heart rate, and respiratory rate. Vital signs are to be obtained prior to collecting laboratory samples
- 12 Lead ECG
- Safety Laboratory Tests
- Serum pregnancy
- Ulcer Assessment: Visual examination of chronic ulcer.
- No debridement to be performed at this visit
- Two wound swabs will be taken, one for microbiological culture and one for microflora examination (unless ulcer has completely re-epithelialized).
- Take digital photos with the digital camera provided by sponsor. Two photos are to be taken from a focal distance of 18 inches, and one photo taken close-up for a total of three digital images
- Employ an advanced digital imaging system to accurately measure the target foot ulcer dimensions.
- Collect kit dispensed on Day 21, perform drug accountability
- Record all adverse events (local and systemic), concurrent procedures, and changes in concomitant medications during the study on the source documents and case report forms (eCRFs).

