# **Brief Trial Description**

This study is a phase 2a, multi-center, double-blind, placebo-controlled, dose-escalating, parallel group, randomized controlled trial designed to evaluate the safety and tolerability of topically applied bisphosphocin NU-3 gel to clinically non-infected Wagner grade 1 diabetic foot ulcers (DFUs).

Two weeks after screening, subjects will be randomized 3:1 to bisphosphocin Nu-3 gel and standard of care (SOC) or placebo gel and SOC to treat Wagner 1 DFUs. Major inclusion criteria will be DFUs between 1.0 and 10 cm^2 initial area and having no wound ischemia.

Subjects will be seen weekly until 6 weeks after randomization unless the subject's wound healed, or the subject is withdrawn or lost to follow-up (i.e., early termination). The bisphosphocin Nu-3 or placebo gel will be applied starting on the day of randomization for 4 weeks twice daily. The study will be executed in two phases: cohort 1 and cohort 2, in which the doses for the intervention group will be 5% or 10% Nu-3 gel.

SOC in this study will be offloading of the DFU using a removable cast walker provided to the subject, appropriate sharp or surgical debridement (note: there will be several rules pertaining to prohibition on certain visits and degree of debridement), and infection management post-randomization as deemed appropriate by the investigator. Primary dressings will be Mepitel (or equivalent), Tegaderm, and padding/Coban Lite 2- layer dressing.

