  - Laboratory evaluations and vital signs assessments will be summarized by dose group (including placebo group) and time point of collection (i.e., visit number starting with randomization visit) (see shell Table 2).
    - Tables will also be constructed for each subject per timeline (see Shell Table 3)

[figure not shown]
SAP: LLA-Nu3-CLIN002 Page 8 of 21

 Table describing change in value and percentage change from baseline for each visit will be provided for vital signs for each subject (see Shell Table 4)

- Table describing out-of-normal range shifts will be provided for clinical laboratory results for each subject, grouped according to dose group (See Shell Table 5)
- Table describing changes noted in physical examinations (at each visit after randomization) will be constructed for each subject, grouped according to dose group (see Shell Table 6)
- Efficacy date will be analyzed as follows:
  - Summary statistics of DFUs that healed by treatment group by 6 weeks (numbers and percentage healed); graph showing weekly percentage of wounds healed by treatment group
  - PAR weekly plot by treatment group; summary table of PAR values by week and treatment group
  - Time to heal within 6 weeks (summary time to heal statistics by treatment group) using Kaplan-Meier method; probability of wound healing (1-survival ≡ 1-wounds not healed) plot by treatment group. If the percentage healed figures for the 5% and 10% Nu-3 groups at 6 weeks is within 10% and a statistical power calculation shows that the proportions of wounds healed for the combined versus placebo groups is at least 80%, the times to heal will be tested using the logrank test.
  - Bacterial counts (CFU/g) for weeks 0-4 will be analyzed by (a) reporting the means and standard deviations for each group at each time point and (b) using GLMM (general linear modeling with repeated measures [weeks 1-4] and counts at week 0 as a factor)
  - Microbiological data will be summarized for each of the 3 treatment groups for each visit (visits 1, 3, 4, 5, 6, 7; unscheduled visit; early termination) as follows (a) list of species detected in each microbiological sample (Shell Table 11); and (b) susceptibility testing to the following drugs for each microbiological sample: penicillin, vancomycin, and linezolid (Shell Table 12)
    - \*A reason will be given in each instance in which susceptibility testing was *not* done (e.g., no growth).

SAP: LLA-Nu3-CLIN002 Page 9 of 21

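### The protocol sets its endpoints at Day 28, but the SAP runs percentage healed, time to heal and the log-rank gate to 6 weeks and is unclear on how a healing first seen at Day 42 counts

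*SAP*

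**What the plan says.** **Protocol.** Section 4 and the matching synopsis table head the endpoint column "Endpoint [at 28 days" for primary and secondary objectives alike. Section 8, under Visit 7, states: "The study subject will return for final efficacy evaluation to the clinical site on Day 28±2 days". Section 7.1 gives the dosing as "Gel to be applied twice daily (BID) for 28 days". The synopsis lists Day 42 as "Safety Follow-up: 42 days (± 2 days) after first treatment", and its Administration paragraph assigns the gels by visit: "Commercially acquired Hydrogel from V1 to V3 and after V7 through V8. Test Product gel between V3 and V7".

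**SAP.** The Brief Trial Description agrees on treatment length: the gel "will be applied starting on the day of randomization for 4 weeks twice daily". The efficacy part of the Analysis section then uses 6 weeks for three items:

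- the healing summary: "Summary statistics of DFUs that healed by treatment group by 6 weeks (numbers and percentage healed";
- time to heal: "Time to heal within 6 weeks (summary time to heal statistics by treatment group) using Kaplan-Meier method";
- the gate for the log-rank test, which first asks whether the 6-week healed percentages of the 5% and 10% groups lie within 10% of each other.

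Under Days to Index Ulcer healing, the SAP calculates days to healing for ulcers that heal in the treatment phase. In the same entry it censors unhealed completers at 42 days.

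**The concern.** The two documents give different time points for judging clinical effect, and the SAP does not explain the change. An ulcer that closes between Day 28 and Day 42 counts in the SAP's healing summary but falls after the protocol's endpoint time and after the last dose.

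The SAP's own rule for time to heal leaves that ulcer in doubt. Read by its first sentence, a Day 42 healing is outside the treatment phase and gets no healing time. Read by its censoring rule, only subjects without a healing event are censored at 42 days, which implies that follow-up for events runs to Day 42. Two analysts could build different Kaplan-Meier curves from the same data.

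At stake are the size of the reported healing contrast, the reproducibility of the time-to-heal analysis and, less often, whether the log-rank test is run. These results feed a stated secondary objective (clinical effects on the ulcer) and the dose recommendation after Cohort 2.

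**Working it through.** The plan gives no healing rate, effect size or power figure, so there is none to reproduce. The check has four steps.

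**1. Length of the off-drug interval.** Nominally 42 − 28 = 14 days, and 14/42 = 33% of the SAP's window. With ±2 days at both visits, it runs from 40 − 30 = 10 days (10/40 = 25%) to 44 − 26 = 18 days (18/44 = 41%).

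**2. When a late healing can be seen.** The SAP describes weekly visits to 6 weeks. The protocol's Schedule of Events has no visit between Day 28 and Day 42. At scheduled visits, therefore, any healing in the interval is first observed at Visit 8, which is exactly where the SAP's event and censoring rules disagree.

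**3. Effect on the healing contrast, under assumptions.** Assume a constant placebo healing hazard λ, a hazard ratio of 2 on Nu-3 up to Day 28 and of 1 afterwards, and placebo healing by 6 weeks of P = 15%, 25% or 40%. Then λ = −ln(1 − P)/42, and:

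- placebo at Day 28 = 1 − exp(−28λ);
- Nu-3 at Day 28 = 1 − exp(−2 × 28λ);
- Nu-3 at Day 42 = 1 − exp(−2 × 28λ − 14λ).

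| P (placebo, Day 42) | Placebo, Day 28 | Nu-3, Day 28 | Nu-3, Day 42 | Healed ratio, Day 28 → 42 | Difference in points, Day 28 → 42 |
|---|---|---|---|---|---|
| 15% | 10.3% | 19.5% | 23.7% | 1.90 → 1.58 | 9.2 → 8.7 |
| 25% | 17.5% | 31.9% | 38.1% | 1.83 → 1.52 | 14.4 → 13.1 |
| 40% | 28.9% | 49.4% | 57.3% | 1.71 → 1.43 | 20.5 → 17.3 |

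The absolute difference shrinks by 0.5, 1.3 and 3.2 points. Between 28% and 32% of placebo healings fall after Day 28; for P = 25%, (25 − 17.5)/25 = 30%.

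**4. Effect on the log-rank gate.** The gate has two parts: the two doses within 10 points at 6 weeks, and at least 80% power for combined Nu-3 versus placebo. I took power from the observed proportions with 24 versus 8 subjects, two-sided at 0.05, which is one reading of the SAP. With 12, 12 and 8 subjects, the same placebo rates, on-drug hazard ratios of 1, 2 and 3, and 40,000 simulated trials per scenario:

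- the full gate gives different answers at Day 28 and Day 42 in about 0.1% to 8.5% of trials, and in at most 2.8% at a hazard ratio of 1 or 2;
- it passes in under 10% of trials at either time point in every scenario.

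Outside that range, with placebo Day 28 healing of 30% and a hazard ratio of 5, power at the assumed true rates is 82% at Day 28 and 70% at Day 42. The 80% condition then passes at one horizon and fails at the other.

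**The case against.** The best defence has four parts.

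- **Healing is not a listed protocol variable.** Those are ulcer area, depth and microbiology; complete healing and time to heal enter with the SAP, and protocol section 12.3.1 leaves the efficacy analysis to it. This stands, so the SAP is not contradicting a protocol healing endpoint. It is measuring the clinical-effects objective, whose endpoints the protocol puts at 28 days, at another time without saying why.
- **Day 42 is not a safety-only visit.** A reader might infer that from the synopsis label. Section 5.5 includes an ulcer evaluation, and the Schedule of Events requires visual examination and imaging at Visit 8. This also stands: a 6-week summary uses data collected on purpose.
- **Week 4 results are already planned.** The weekly area-reduction table, the weekly healed-percentage graph and the bacterial counts all cover week 4. True; only the healing summary, the Kaplan-Meier analysis and the gate are affected.
- **A fixed 6-week horizon from randomization is legitimate.** It applies equally to all arms and yields more events in a 32-subject pilot. Stating and justifying it in both documents would also settle the mismatch. It would still leave the conflict within the SAP's time-to-heal rule to be corrected.

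**Conclusion.** The mismatch between the documents and the SAP's unclear handling of a Day 42 healing rest on the text alone. The size of any effect on the results rests on assumptions.

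Two stronger readings are tempting, and the documents support neither. One is that the off-drug days necessarily dilute the treatment effect. That requires the effect to stop with the gel, and the documents do not say. If the effect persists or is delayed, the direction could differ. Even under the stopping assumption at a hazard ratio of 2, the absolute difference falls by only 0.5 to 3.2 points.

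The other is that the horizon often decides whether the healing test is run. The dose-similarity condition taken alone does change its answer in 18% to 32% of the simulated trials. But it is only half the gate, and its largest figure occurs with no drug effect at all, so it mostly reflects small numbers. The full gate changes in about 0.1% to 8.5%.

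The point is minor: the output is secondary and mainly descriptive, and the SAP tests no primary hypothesis.

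**What to change.** In the SAP:

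- Make Day 28 (Visit 7) the main time point for number and percentage healed.
- Run the Kaplan-Meier and log-rank analysis to Day 28, censoring unhealed subjects who reach Visit 7 at the Visit 7 date. Keep the existing rule for those who leave earlier.
- Take both parts of the log-rank gate, including the 5% versus 10% comparison, from Day 28.
- Rewrite the Days to Index Ulcer healing entry so that the event period and the censoring time both end at Visit 7.
- Report Day 42 healing as a separate summary labelled as off-treatment follow-up.

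The cost is SAP wording and one truncation date, with no new data or visits. The downside is fewer healing events in the main summary; the Day 42 figures remain available beside it.

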#### General

Descriptive statistical methods will be used to summarize the data from this study. These include number of subjects (n), mean and standard deviation (SD) for continuous variable data (medians and IQR [interquartile range] values will be given when the distribution of variable values is non-normal), and frequencies and percentages for categorical variable data. There will be no hypothesis testing performed. All data collected during the study will be reported and analyzed.

Unless specified otherwise, all statistical testing will be two-sided and performed using a significance (alpha) level of 0.05.

All statistical analyses will be conducted using PASW 27 (SPSS; IBM).

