#### **Sample Size Calculations**

Since this is a pilot study focusing primarily on safety, no sample size calculations will be done. Based on general experience with phase 2a trials, it is planned to enroll 32 subjects (24 active and 8 placebo).

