#### Statistical methodology

#### Missing data

\*For calculation purposes, days to healing = date ulcer is first healed – date of randomization.

SAP: LLA-Nu3-CLIN002 Page 6 of 21

Missing data may be the result of missed visits, subjects lost to follow-up or who have died, and may be endpoint data or covariate data. Missing continuous outcome data will be imputed in this study using the LOCF (last observation carried forward). If wound healing outcomes are missing these will be imputed as follows: (a) If an event removes the index ulcer, such as an amputation, the outcome will be scored as not healed; (b) If a subject dies, the outcome will be scored as not healed; (c) If a subject is withdrawn from the study, the outcome will be scored as not healed; and (d) for all remaining non-healed index ulcers in the drug groups, the outcomes will be based on non-right-censored outcomes in the SOC group to weight outcomes.

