#### Research hypotheses

Because this trial is focused on safety, no primary research hypotheses (hypotheses tested using statistical tests) will be tested. However, two secondary endpoints will be tested statistically, one of which has to meet a priori conditions to decide validity of testing.

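### Whether the log-rank test of time to heal is run depends on two conditions computed from this trial's own healing results

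*SAP*

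**What the plan says.** The SAP's Research hypotheses section says that two secondary endpoints will be tested, "one of which has to meet a priori conditions to decide validity of testing". The only such conditions are in the efficacy part of the Analysis section, under time to heal within 6 weeks. The log-rank test is run when both of these are met:

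1. "If the percentage healed figures for the 5% and 10% Nu-3 groups at 6 weeks is within 10" per cent.
2. "a statistical power calculation shows that the proportions of wounds healed for the combined versus placebo groups is at least 80" per cent. The sentence is garbled. I read it as requiring at least 80% power for the comparison of proportions healed, combined Nu-3 against placebo.

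Three other SAP sections bear on this:

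- Sample Size Calculations: "Since this is a pilot study focusing primarily on safety, no sample size calculations will be done". Protocol section 12.1 likewise reports that none was done.
- Missing data, on healing outcomes: "If a subject is withdrawn from the study, the outcome will be scored as not healed". For the remaining non-healed ulcers in the drug groups, "the outcomes will be based on non-right-censored outcomes in the SOC group to weight outcomes".
- General: "There will be no hypothesis testing performed". The next paragraph nevertheless states that, unless specified otherwise, "all statistical testing will be two-sided and performed using a significance (alpha) level of 0.05".

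**The concern.** The rule and its thresholds are fixed in advance, but what goes into them is outcome data. Condition 1 compares this trial's 6-week healing percentages. Condition 2 needs two healing rates, and neither document supplies any other than those the trial will observe. With fixed planning rates the answer would be known before any data, and no condition would be needed.

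Power at the observed rates is a function of the same healing data as the test. It says nothing about whether a log-rank test is valid. Two consequences follow: a planned secondary comparison is lost in many trials where the drug works, and a p-value that does appear has been selected on the strength of the result.

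Condition 1 looks like a check before pooling the doses, but 12 subjects per dose is too few for it to separate equal from unequal doses well. The SAP does not say whether the 10% is in percentage points or relative, and it names no power formula. Two analysts following it in good faith could disagree on whether to run the test. The imputation rules in Missing data can also change the healed percentages used in both conditions.

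**Working it through.** **Inputs.** Group sizes are 12 and 12 on Nu-3 and 8 on placebo (Protocol section 5.1; SAP, Sample Size Calculations). Alpha is 0.05 two-sided (SAP, General). Time to heal is censored at 42 days (SAP, Days to Index Ulcer healing), with assessments on Days 7, 14, 21, 28 and 42 (Protocol section 9). The plan has no derived figure to reproduce: 80% is a threshold, and the 32 subjects rest on general experience. Healing rates are my assumptions. The power formula is not named, so I used four: pooled z, unpooled z, arcsine and exact Fisher. Unless stated otherwise, doses are equally effective, nobody drops out, and the 10% is in absolute points.

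**Condition 1 alone.** One subject is 1/12 = 8.3 points and two are 16.7, so the doses may differ by at most one healed ulcer. The pass probability is the sum of b(i; 12, p1) × b(j; 12, p2) over |i − j| ≤ 1.

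- Both doses 50%: (2,704,156 + 2 × 2,496,144) / 2^24 = 0.459, so identical doses fail 54% of the time.
- Both doses 20%: 0.562, so they fail 44% of the time.
- 40% and 60%: passes 30%. 35% and 65%: passes 17%.

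**Condition 2 alone.** With the pooled formula, power = Φ[(d − 1.96 × se0) / se1], where se0 uses the pooled proportion and se1 the separate ones.

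- 16/24 vs 1/8: d = 0.542, se0 = 0.204, se1 = 0.151, power = 0.826 (pass).
- 12/24 vs 0/8: d = 0.500, se0 = 0.198, se1 = 0.102, power = 0.865 (pass); 11/24 gives 0.779 (fail).

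Under this formula every passing outcome already has p ≤ 0.011 (z test) or p ≤ 0.014 (Fisher) for proportions healed. The other formulas move the threshold. Against 0/8 on placebo the condition opens at 12/24 (pooled, Fisher), 8/24 (arcsine) or 6/24 (unpooled). Against 2/8 it opens at 18 to 20 of 24.

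**Both conditions together.** I summed exact binomial probabilities over all outcomes, and simulated the unconditional log-rank with constant healing hazards (100,000 trials per scenario). Ranges cover the four formulas.

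| Healing, Nu-3 vs placebo | Test is run | Unconditional log-rank rejects |
|---|---|---|
| 50% vs 20% | 5-12% | 26% |
| 60% vs 20% | 11-19% | 47% |
| 70% vs 20% | 20-30% | 69% |
| 80% vs 20% | 36-43% | 88% |
| 70% vs 30% | 11-18% | 48% |
| 80% vs 40% | 14-18% | 53% |

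For extreme effects the test is run more often: 62-64% at 90% vs 20%, and 81-83% at 95% vs 20%.

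**Sensitivity.**

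- Relative reading of the 10% (difference at most 10% of the larger percentage): 2-5%, 5-9%, 13-20% and 33-39% for the first four rows.
- 10% of each arm withdrawing and scored not healed multiplies each rate by 0.9 (70% vs 20% becomes 63% vs 18%). The test is then run in 15.0-24.5% of trials at 70% vs 20% and 25.5-34.6% at 80% vs 20%.

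**No effect (30% in all groups).** Both conditions are met in 0.2-2.4% of trials. Test-and-reject is 0.2-0.7%, against 4.6% for the unconditional test. Given that the test is run, it rejects in 100% (pooled, Fisher), 46% (arcsine) or 28% (unpooled) of cases. Across common rates of 20% to 50% that conditional figure runs from 8% to 100%, and test-and-reject from 0.1% to 1.1%, against 4.0-5.3% unconditional.

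**The case against.** The strongest reply is that this is a 32-subject safety pilot with a rule written before analysis. The rule does not inflate type I error, and percentages healed and Kaplan-Meier summaries are reported either way. What is lost is one exploratory p-value. All of that is true, and it limits how serious the point is. It does not make the rule sound.

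Other objections:

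- **The inputs to condition 2 are inferred.** Correct, but observed rates are the only ones available. If planning rates were meant, the SAP omits them. Condition 1 depends on outcomes on any reading.
- **The no-effect range of 28-100% is for one healing rate and a rare event.** Correct. At 20% healing with the unpooled formula the figure is about 8%, close to nominal, and the test is run in few no-effect trials.
- **The table compares running the test with rejecting.** Correct, but it matters little. At 50% vs 20% with the unpooled formula the test is run in 11.7% of trials, and run and significant in about 10%.
- **Condition 1 gives some protection against pooling unlike doses.** It does: with 40% and 70% vs 20%, both conditions are met in only 2.8-5.5% of trials. But it also blocks identical doses about half the time. Showing the doses separately deals with the problem without suppressing the comparison.

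**Conclusion.** The concern holds and should be fixed. The log-rank test is conditional on this trial's healing results, and calling the conditions a priori checks on validity does not describe them correctly. At assumed healing of 50% to 80% on both doses against 20% on placebo, the test is run in 5% to 43% of trials, where an unconditional test would reject in 26% to 88%. When the test is run under no effect, its p-value usually cannot be read at face value, although overall the procedure is conservative.

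The size rests on assumed healing rates, full enrolment at 12/12/8, equal dose effects, observed rates as the input to the power calculation, and absolute points for the 10%. The direction is the same under the relative reading and with 10% withdrawal. Separately, the statement in General that no hypotheses are tested contradicts Research hypotheses and Analysis. No safety, dose-escalation or primary conclusion depends on any of this.

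**What to change.** In the SAP's Analysis section, replace the conditional sentence with:

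> Time to heal will be compared between combined Nu-3 and placebo with one two-sided log-rank test, reported whatever the result and labelled exploratory, with a hazard ratio and 95% CI. Kaplan-Meier curves and percentages healed with 95% CIs will be shown separately for 5% Nu-3, 10% Nu-3 and placebo.

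Add that if no placebo ulcer heals, the difference in proportion healed with its 95% CI replaces the hazard ratio, which is then not estimable. At 20% placebo healing the chance of this is 0.8^8 = 17%. The log-rank result is still reported. The existing censoring rule (Days to Index Ulcer healing) and Patient Populations apply to this test; a cross-reference to both would avoid doubt.

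Delete the reference to a priori conditions from Research hypotheses, and change General to say that no confirmatory testing is done. That wording also fits the baseline comparisons planned in Analysis. If General is to stand as written, drop the log-rank and report Kaplan-Meier estimates with 95% CIs.

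The cost is SAP wording only. There are two downsides. The result will often be imprecise and non-significant: the unconditional test rejects only 47% of the time at 60% vs 20%. And a pooled estimate is harder to read if the doses differ: with 40% and 70% vs 20%, the pooled 55% describes neither dose and the test rejects 36% of the time. The separate curves make such a difference visible, and the exploratory label limits the claim.
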